8.6 PHARMACODYNAMICS/EXPLORATORY BIOMARKERS

Blood and tissue samples will be collected as specified in the SoA (Section 1.3). The date and time of each sample collection should be recorded in the eCRF. Details on processes for collection and shipment of these samples can be found in the Laboratory Flow Chart.

These samples will be tested for protein, nucleic acid, or other tissue or blood derived biomarkers relating to the proposed mechanism of action of RO7121661. These include, but are not limited to, drug RO, cellular profile and activation status of immune cells in blood and tumor, cytokines and other soluble markers of inflammation. Analysis techniques may include, but are not limited to, flow cytometry, immunohistochemistry, gene expression, and gene sequencing. DNA and/or RNA will be extracted for exploratory research on genetic biomarkers (including, but not limited to, cancer-related genes and biomarkers associated with common molecular pathways, or immunemediated markers, microsatellite instability (MSI) and tumor mutational burden), and to enable genomic analysis for exploratory research on genetic biomarkers.

The specimens will also be used for research purposes to identify biomarkers useful for predicting and monitoring response to RO7121661 treatment, identifying biomarkers useful for predicting and monitoring RO7121661 safety, assessing PD effects of RO7121661 treatment, and investigating mechanism of therapy resistance. This may include retrospective and longitudinal testing of bacterial or viral infection (including but

not limited to SARS-CoV-2) by serological methods. These analyses may inform any association of bacterial or viral infection and response to treatment.

Additional markers may be measured in case a strong scientific rationale for these analyses develops. Any remaining samples after the specified analyses may also be used for additional (assay) validation experiments. Samples may be used for research to develop methods, assays, prognostics and/or companion diagnostics related to RO7121661, disease process, pathways associated with disease state, and/or mechanism of action of the study treatment. Note that as science and research is evolving, the list of biomarkers that will be evaluated cannot be fully defined.

Based on continuous analysis of data any sample type, time point, and/ or analysis not considered to be critical for safety may be stopped at any time if the data does not support a strong scientific justification to continue. During the course of the study, sampling time-points may be modified on the basis of emerging data to ensure the PD of RO7121661 can be adequately characterized (but without increasing overall blood collection volume). This will be documented in a Note to File and a new SOA will be provided.

Archival tumor blocks will be returned, unless notified by the site that they do not want it back. Blood, tissue and other residual material (slides, extracts, on-study blocks, etc.) will be destroyed within 2 years after the final closure of the clinical database unless the participant gives specific consent for the remainder of the material to be stored for optional exploratory research (RBR).

When a participant withdraws from the study, samples collected prior to the date of withdrawal may still be analyzed, unless the participant specifically requests that the samples be destroyed or local laws require destruction of the samples. However, if samples have been tested prior to withdrawal, results from those tests will remain as part of the overall research data.

Data arising from all biosamples including samples for analyses of inherited DNA will be subject to the confidentiality standards described in Appendix 1 Section 1.4.

8.6.1 Blood Samples

The following samples for PD and biomarker research are required and will be collected from all participants in this study:

- Blood samples will be collected for measurement of RO during dose escalation.
- Blood samples will be collected for measurement of cytokines/chemokines (e.g., IL-2, IL-6, IL-8, and IFN_γ) and immune activation markers such as sCD25
- Blood samples will be collected for measurement of soluble target (PD-1, TIM-3)
- Blood samples will be collected for the measurement of IgE/Tryptase

• Blood for whole genome sequencing (see Section 8.7.1). If this sample is missing on Cycle 1 Day 1, it should be collected at the next scheduled visit, where possible

The following additional samples for PD and biomarker research are required and will be collected from Part B participants only

- Blood samples will be collected for flow cytometry. The samples will be analyzed for changes in the numbers and activation status of lymphocyte subsets including but not limited to CD4+, CD8+, and/ or NK cells
- Blood for RNA extraction will be collected for gene expression analysis
- Blood for bTMB
- Blood for ctDNA

8.6.2 Tissue Samples

8.6.2.1 Archival Tumor Samples

FFPE archival tumor tissue is to be obtained from all participants, if available. The primary and the most recent metastasis (if both are available) should be submitted for analysis. Ideally these samples should include the invasive margin. Tumor blocks are preferred but slides will be accepted. Samples will be collected for IHC and immunofluoresence analyses (such as, but not limited to, CD8/Ki67, PD-1, TIM-3, PD-L1). Samples may also be used for TMB or gene expression.

Archival tumor blocks will be returned to the sites when requested by the investigator or at the end of the study, unless notified by the site that they do not want it back.

8.6.2.2 Fresh Tumor Biopsies

Screening and on treatment fresh tumor biopsies may be required for additional participants (i.e., if dose cohort extended to confirm safety, PK and/or RO and/or the biomarker profile) in Part A1 and A2, unless otherwise specified by the Sponsor. In Part B, screening and on treatment biopsies are mandatory in all cohorts. In order to mitigate the potential risk associated with tumor biopsies, all participants required to have a biopsy must have tumor lesions from which biopsies can be safely obtained, as per clinical judgment of the treating physician.

The screening sample should be collected after eligibility is confirmed unless the fresh biopsy sample is needed to confirm patient eligibility (e.g. to confirm PD-L1 expression levels for Cohorts B2 and B3). Post dose samples can be collected +2/-1 day from scheduled time-point. If the participant progresses and discontinues treatment prior to on treatment biopsy day, the tumor biopsy should be taken at the time of treatment discontinuation. An additional biopsy at the time of partial response, stable disease, progression or at any other time-point of interest based on participants' course of disease may be taken after discussion between the Investigator and the Sponsor.

Use of available existing biopsies at the sites prior to the participant's entry in the study should be discussed with the Sponsor (i.e., biopsy should have recently been obtained as part of diagnosis biopsy and participants should have not received any tumor treatment after this collection).

Collection of tumor biopsies should be guided by ultrasound, CT scan, or other methods according to the location of the selected lesion using a 16-gauge needle (preferred) to provide cores, ideally, of at least 20 mm in length or equivalent size. Ideally 4 (minimum 2) core biopsies will be obtained at each time-point (at the physician's discretion). Fine-needle aspiration is not acceptable. The biopsies will be taken from accessible tumor locations, including, but not limited to, skin, lymph node, rectum, liver etc. Bone biopsies and trans-bronchial biopsies are not acceptable.

If feasible, on-treatment biopsies may be repeated if the initial biopsy did not contain sufficient tumor material for analysis. The location of each biopsy will be documented in relation to each tumor lesion as determined by imaging. The baseline and on-treatment biopsies should be preferably taken from the same tumor lesion (metastasis) to ensure comparability. If the sample cannot be collected from the same lesion (e.g., lesion disappears after treatment) then preferably the biopsy should be collected from the same organ, if possible.

Additional participants may be enrolled in Part B in the event that paired fresh baseline and on-treatment biopsies are not evaluable for the key biomarker analyses to ensure that at least 60% of paired fresh biopsy samples are evaluable to conclude the PD analysis.

In the event that a fresh biopsy is taken during the screening period and the participant is not enrolled into the study, the fixed and embedded biopsy (FFPE block) can be returned to the site upon site request. The site must confirm that a written consent is obtained from the participant before return request submission to Roche. If the participant does enroll in the study, fresh biopsies will not be returned to the site.

Biopsies will be used for IHC (e.g., CD8/Ki67, PD-1, TIM-3, PD-L1), TMB and gene expression.

8.7 GENETICS

8.7.1 Whole Genome/Exome/Targeted DNA Analysis

At participating sites, blood samples will be collected for DNA extraction to enable whole genome sequencing (WGS) to identify mutations that are predictive of response to study drug, are associated with progression to a more severe disease state, are associated with acquired resistance to study drug, are associated with susceptibility to developing adverse events, can lead to improved adverse event monitoring or investigation, or can increase the knowledge and understanding of disease biology and drug safety. The DNA may also be used to determine if alleles at genes associated with immunity, such

as KIR and HLA alleles, affect the PK/PD/efficacy/safety of the treatment. Research may distinguish germline mutations from somatic mutations. The samples may be sent to one or more laboratories for analysis.

Collection and submission of WGS samples is contingent upon the review and approval of the exploratory research by each site's Institutional Review Board or Ethics Committee (IRB/EC) and, if applicable, an appropriate regulatory body. If a site has not been granted approval for WGS sampling, this section of the protocol will not be applicable at that site.

Genomics is increasingly informing researcher's understanding of disease pathobiology. WGS provides a comprehensive characterization of the genome and, along with clinical data collected in this study, may increase the opportunity for developing new therapeutic approaches or new methods for monitoring efficacy and safety or predicting which participants are more likely to respond to a drug or develop adverse events. Data will be analyzed in the context of this study but will also be explored in aggregate with data from other studies. The availability of a larger dataset will assist in identification and characterization of important biomarkers and pathways to support future drug development.

Blood samples collected for WGS are to be stored until they are no longer needed or until they are exhausted. However, the storage period will be in accordance with the IRB/EC approved Informed Consent Form and applicable laws (e.g., health authority requirements).

Participant medical information associated with WGS samples is confidential and may be disclosed to third parties only as permitted by the Informed Consent Form (or separate authorization for use and disclosure of personal health information) signed by the participant, unless permitted or required by law.

Given the complexity and exploratory nature of the WGS analyses, data derived from these analyses will generally not be provided to study investigators or participants unless required by law. The aggregate results of any conducted research will be available in accordance with the effective Sponsor policy on study data publication.

8.8 SAMPLES FOR RESEARCH BIOSAMPLE REPOSITORY

8.8.1 Overview of the Research Biosample Repository

The Roche Research Biosample Repository (RBR) is a centrally administered group of facilities for the long-term storage of human biologic specimens, including body fluids, solid tissues, and derivatives thereof (e.g., DNA, RNA, proteins, peptides). The collection, storage and analysis of these specimens will facilitate the development/assessment of new pharmaceutical agents and the development of diagnostic tests, which may allow for individualized drug therapy for participants in the future.

Specimens will be collected from participants who give specific consent to participate in this optional Research Biosample Repository. Collected specimens will be used to achieve the following objectives:

- To study the association of biomarkers with efficacy, adverse events, or progressive disease.
- To increase knowledge and understanding of disease biology.
- To study treatment response, including drug effects and the processes of drug absorption and disposition.
- To develop biomarker or diagnostic assays and establish the performance characteristics of these assays.

8.8.2 Sample Collection

The following samples will be collected for identification of genetic (inherited) biomarkers:

Saliva for DNA extraction

Saliva will be collected to assess comparability of DNA extraction from saliva and whole blood. This collection will serve as a pilot for an overall strategy to decrease participant burden and blood volume collection for DNA extraction in exploratory research.

The following samples will be stored in the RBR and used for research purposes, including, but not limited to, research on biomarkers related to RO7121661 or diseases:

- Leftover blood samples
- Leftover tissue samples

The samples collected for DNA extraction may be sent to one or more laboratories for analysis of germline or somatic mutations via whole genome sequencing (WGS), whole exome sequencing (WES), next-generation sequencing (NGS), or other genomic analysis methods.

Genomics is increasingly informing researcher's understanding of disease pathobiology. WGS provides a comprehensive characterization of the genome and, along with clinical data collected in this study, may increase the opportunity for developing new therapeutic approaches. Data will be analyzed in the context of this study but will also be explored in aggregate with data from other studies. The availability of a larger dataset will assist in identification of important pathways, guiding the development of new targeted agents.

Samples may be sent to one or more laboratories for analysis for WGS and other genomic analyses and associated clinical data may be shared with researchers who are not participating in the study or submitted to government or other health research databases for broad sharing with other researchers. Participant will not be identified by

name or any other personally identifying information. Given the complexity and exploratory nature of these analyses, WGS data and analyses will not be shared with investigators or study participants unless required by law.

For all samples, dates of consent and specimen collection should be recorded on the associated RBR page of the eCRF. For sampling procedures, storage conditions, and shipment instructions, see the separate Laboratory Manual.

RBR specimens will be stored and used until no longer needed or until they are exhausted. The Research Biosample Repository storage period will be in accordance with the IRB/EC-approved Informed Consent Form and applicable laws (e.g., Health Authority requirements).

The repository specimens will be subject to the confidentiality standards (as described under Confidentiality and in Appendix 1).

8.9 HEALTH ECONOMICS

Health Economics/Medical Resource Utilization and Health Economics parameters are not evaluated in this study.

8.10 TIMING OF STUDY ASSESSMENTS

8.10.1 Screening and Pre-treatment Assessments

Written informed consent for participation in the study must be obtained before performing any study-specific screening tests or evaluations. Informed Consent Forms (ICFs) for enrolled participant and for participants who are not subsequently enrolled will be maintained at the study site.

All screening and pre-treatment assessments must be completed and reviewed to confirm that participants meet all eligibility criteria. The Investigator will maintain a screening log to record details of all participants screened and to confirm eligibility or record reasons for screening failure.

An Eligibility Screening Form (ESF) documenting the Investigator's assessment of each screened participant with regard to the protocol's inclusion and exclusion criteria is to be completed by the Investigator and kept at the investigational site.

Screening and pre-treatment assessments will be performed within 28 days prior to Cycle1 Day 1 unless otherwise specified. Results of standard-of-care tests or examinations performed prior to obtaining informed consent and within 28 days prior to Cycle1 Day 1 may be used (and do not need to be repeated for screening) unless indicated in the SoA (see Section 1.3).

8.10.2 Assessments during Treatment

Under no circumstances will participants who enroll in this study and have completed treatment as specified, be permitted to re-enroll in the study.

All assessments must be performed as per SoA (see Section 1.3). Assessments scheduled on the day of study treatment administration should be performed prior to administration of study treatment, unless otherwise noted in the schedule of assessments.

8.10.3 Assessments at Study Completion/Early Termination Visit

Participants who complete the study or discontinue from the study early will be asked to return to the clinic 28 days (± 7 days) after the last dose of study drug for a follow-up visit (see Section 1.3). The visit at which response assessment shows progressive disease may be used as the study completion/early termination visit.

8.10.4 Follow-Up Assessments

Participants will be treated with study treatment, until disease progression, unacceptable toxicity, or withdrawal of consent. Participants may continue study treatment for 24 months or longer if the participant is still benefitting from treatment at the time of last visit at the end of the two-year period.

As with other immunotherapies, treatment beyond RECIST progression could be considered after approval by the Sponsor. The criteria needed for continuing treatment beyond initial apparent progressive disease per RECIST Version 1.1 (e.g., radiological progression secondary to tumor inflammation, TLS) are outlined in Section 7.1.

After the study completion/early termination visit, adverse events should be followed as outlined in Sections 8.3.1 and 8.3.3.

8.10.4.1 Post-Study Safety Follow-up

The sites will provide to the Sponsor an update on safety status 60 days (±7 days) after last treatment for Part A and 90 days (±7 days) after last treatment for Part B.

8.10.4.2 Post-study Survival Follow-up

The sites will provide to the Sponsor an update on survival status 90 days (±7 days) after last treatment and then every 3 months thereafter up until 24 months (48 months for the extended treatment period) post initial treatment for each participant enrolled in the study. Contact can be either in person or via a phone call to document; the sites will use a designated section of the eCRF for this purpose.

8.10.5 Assessments at Unscheduled Visits

Please see Section 1.3 for activities that are required to be performed in case of an unscheduled visit. For an unscheduled visit in the event of an IRR or hypersensitivity

event≥Grade 2 or AE leading to dose reduction or delay, please see Section 8.3.8.1 and Appendix 6.

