Participants will be treated with RO7121661 until disease progression, unacceptable toxicities, or withdrawal of consent. Participants may continue treatment with RO7121661 for 24 months or longer if the participant is still benefitting from treatment at the time of the last visit at the end of the two-year period. As with other immunotherapies, treatment beyond progressive disease according to RECIST Version 1.1 can be considered after consultation and agreement between the Sponsor and Investigator.

Length of Study

The duration of the study for each participant will be up to 27 months (Parts A and B), divided as follows:

Screening: Days -28 to -1

Treatment Period: Cycle 1 Day 1 to Month 24 (may be modified if supported by emerging data). Safety follow-up: $60~(\pm~7)$ days after last treatment with RO7121661 for Part A; $90~(\pm~.7)$ days after last treatment with RO7121661 for Part B.

Survival follow-up: 90 (\pm 7) days after last treatment with RO7121661; then every 3 months (\pm 2 weeks) for total 24-month study period after initial dose.

The treatment period may be prolonged past month 24 if the participant is still benefitting from treatment at the time of the last visit at the end of the two-year period. Participants may extend treatment within the ongoing study whether they are on treatment or are on a treatment pause at the 24-month time point. During the extended treatment period, the participant follows the schedule of assessments as indicated for "Subsequent Cycles." Participants will be treated until disease progression, unacceptable toxicities, or withdrawal of consent. For participants who extend their treatment, the safety follow-up will be performed $60 (\pm 7)$ days for Part A or $90 (\pm 7)$ days for Part B after the last treatment with RO7121661 and survival follow-up every 3 months $(\pm 2$ weeks) thereafter for a total of 48 months after initial dose, or end of the study.

End of Study

The end of the study is defined as the last participant's last visit (LPLV) per protocol (includes the safety follow-up visit 60 days (Part A) or 90 days (Part B) after last dose of study drug) or the date at which the last data point from the last participant required for statistical analysis is received (last participant, last observation), whichever is the latest date. Because of the exploratory nature of this clinical study, any part of its conduct can be discontinued at any time at the discretion of the Sponsor.

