- 10. Lipid panel is to be obtained at Screening, Cycle 1, Day 1 and then every 8 weeks (±7 days) after Cycle 1/Day 1 and at indicated time-points.
- 11. Serum pregnancy test at screening, within 7 days prior to first dose, every cycle (urine or serum), discontinuation visit, and at the safety follow-up visit; a urine or serum pregnancy test will be performed. If a urine pregnancy test is positive, it must be confirmed by a serum pregnancy test. Results must be obtained and reviewed prior to administration of RO7121661. Unscheduled pregnancy test (urine or serum) can be done anytime during the study if clinically indicated.
- 12. Participants who discontinue will be asked to return to the clinic for an early termination visit within 28 (± 7) days after the last dose. In some instances, the visit at which a response assessment shows progressive disease may be used as the early termination visit.

 Alternatively, the study completion visit may be completed at the end of study if a participant remains on a treatment pause to that day.
- 13. Survival follow-up visit to be performed 90 (± 7) days after the last treatment either in person or a phone call to document any ongoing or resolved AEs, and every 3 months (± 2 weeks) thereafter up to 24 months (48 months for the extended treatment period) from 1st dose for overall survival. For participants in Part B, the safety follow-up visit will occur on the same day as the first survival follow-up visit. Post-study anti-cancer therapies should be collected and reported as appropriate in the electronic case report form (eCRF).

Table 1 Schedule of Activities: Q2W regimen for Part A and B1, 2, 3, 4, and 5 (cont.)

- 14. Vital signs include measurements of heart rate, respiratory rate, systolic and diastolic blood pressures (while the patient is in a supine position), and temperature. For each visit, only those vital signs that are obtained prior to study drug administration or that constitute an adverse event (e.g., temperature for event of fever) or a primary manifestation of an adverse event (e.g., blood pressure associated with an infusion-related reaction or heart rate associated with an arrhythmia) should be recorded in the eCRF.
- 15. At Screening, an immunology sample will be taken for quantitative immunoglobulins (Ig): IgA, IgG, IgM, and IgE.

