	 PFS defined as the time from the first study treatment (Day 1) to the first occurrence of progression per Investigator assessment or death from any cause, whichever occurs first.
 To make a preliminary assessment of overall survival from RO7121661 (Part A and B). 	 Overall survival (OS), defined as the time from first study treatment to death from any cause (if data mature at the time of analysis).
To explore and identify potential PD biomarkers in association with exposure kinetics (Part A and B).	 Examine PD changes in the following compartments:
	 Tumor Microenvironment (pre– and on-treatment tumor biopsies): Measure changes in degree and extent of T-cell infiltration and inflammatory gene expression profiles/signatures.
	 Peripheral Blood: Serial sampling to assess kinetic changes in select T-cell subsets, inflammatory cytokines, soluble factors, gene signatures and monitoring tumor burden.
 Correlation of anti-tumor activity of RO7121661 to PK, PD and safety (Part A and B). 	 Compare anti-tumor activity by RECIST with PK parameters, PD changes and safety events.

ADAs = anti-drug antibodies; AEs = adverse events; ctDNA = circulating tumor DNA; DCR = Disease control rate; DLTs = dose-limiting toxicities; DoR = Duration of response; iRECIST = immune-related RECIST; IV = intravenous; MTD = maximum-tolerated dose; NCI CTCAE = National Cancer Institute Common Terminology Criteria for Adverse Events v5.0; ORR = Objective response rate; OS = Overall survival; PD = pharmacodynamics; PFS = Progression free survival; PK = pharmacokinetic; RDE = recommended dose for expansion; RECIST = Response Evaluation Criteria in Solid Tumors; RO = receptor occupancy; RR = response rate; SD = stable disease; SDR = stable disease rate; TMB = tumor mutational burden.

4. STUDY DESIGN

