4.1.1 Length of the Study

The duration of the study for each participant will be up to 27 months (Parts A and B), divided as follows:

- Screening: Days 28 to 1
- Treatment Period: Cycle 1 Day 1 to Month 24 (may be modified if supported by emerging data).
- Safety follow-up: 60 (\pm 7) days after last treatment with RO7121661 for Part A; 90 (\pm 7) days after last treatment with RO7121661 for Part B.
- Survival follow-up: 90 (\pm 7) days after last treatment with RO7121661; then every 3 months (\pm 2 weeks) for total 24-month period after initial dose.

The treatment period may be prolonged past month 24 if the participant is still benefitting from treatment at the time of the last visit at the end of the two-year period. Participants may extend treatment within the ongoing study whether they are on treatment or are on a treatment pause at the 24-month time point. During the extended treatment period, the participant follows the SoA as indicated for "Subsequent Cycles." Participants will be treated until disease progression, unacceptable toxicities, or

withdrawal of consent. For participants who extend their treatment, the safety follow-up will be performed 60 (\pm 7) days for Part A or 90 (\pm 7) days for Part B after the last treatment with RO7121661 and survival follow-up every 3 months (\pm 2 weeks) thereafter for a total of 48 months after initial dose, or end of the study.

4.1.2 Dose-Escalation Decision Criteria

For Part A, RO7121661 dose-escalation will be carried out according to a mCRM with EWOC design and will be based on the occurrence of DLTs. The dose-toxicity relationship is described by a 2-parameter logistic regression model, where the probability of DLT is expressed as a function of dose. The model is continuously updated as additional participant information becomes available (for further information see Appendix 10).

A minimum of participants per cohort will be enrolled and treated in a sequential manner with one week between the first and second participant and at least 2 days between subsequent participants. However, if the first participant experiences a DLT within the first week, then the time between the treatment of subsequent participants within the same cohort may be increased.

A new cohort can be opened when at least participants per cohort are considered DLT evaluable, i.e., if they received 2 doses and either:

- experienced a DLT within the DLT period
- cleared the DLT period without a DLT

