9.4.2 Efficacy Analyses

The primary and secondary efficacy analyses listed in Table 8 will include all participants in the efficacy population with participants grouped according to dose cohort within each study part.

Table 8 Efficacy Statistical Analysis Methods

Endpoint	Statistical Analysis Methods
According to RECIST Version 1.1 criteria and iRECIST:	No formal statistical model and no formal hypothesis testing are planned in this study. Tumor response data will be reported using descriptive statistics. Response data will be listed. ORR and DCR will be summarized by using relative frequencies and 90% confidence interval (CI). If data are sufficient, duration of response and PFS will be summarized by using time-to-event analyses and Kaplan-Meier curves. The above analyses will be carried out for RECIST Version 1.1 (primary analysis) and iRECIST (exploratory analysis).
Overall Survival (OS)	OS data may be tabulated and summarized using time-to-event analyses and Kaplan-Meier curves if data is collected and mature.
	Eventually, summaries will be carried out by cohort separately for each part.

Objective response rate (ORR) and disease control rate (DCR) are determined as the rate of participants with an objective tumor response of CR or partial response (PR) (ORR) or CR, PR or stable disease [SD] (DCR). For this protocol, confirmation of response is required at least 4 weeks after a first response occurred. To classify a response as SD, measurements will have to be classified as stable (according to RECIST Version 1.1) at least once at a minimum of 4 weeks after study entry.

In the primary analysis ORR and DCR will be derived for RECIST Version 1.1 and will be based on Investigators' assessment. Participants with missing or no response assessments will be classified as not evaluable unless there is documented clinical deterioration, in which case participant will be classified as non-responders.

DoR will be calculated for participants who have a best (confirmed) overall response of CR or PR and will be defined as the time from first occurrence of a documented response until the time of documented disease progression or death (death within 30 days from last study treatment) from any cause, whichever occurs first. Censoring methods will be the same as the one applied for progression-free survival (PFS).

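### By-cohort Kaplan-Meier OS has no time limit, but survival contact after month 24 is scheduled only for treatment extenders, so the late curve may not be interpretable as cohort survival

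*Combined protocol and SAP*

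**What the plan says.** Follow-up. Section 8.10.4.2 asks sites for a survival update 90 days after the last dose and then "every 3 months thereafter up until 24 months (48 months for the extended treatment period) post initial treatment for each participant enrolled". The Synopsis ("for total 24-month study period after initial dose") and Table 1 footnote 13 ("thereafter up to 24 months (48 months for the extended treatment period) from 1st dose for overall survival") agree.

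Who gets 48 months. Section 4.1.1: "The treatment period may be prolonged past month 24 if the participant is still benefitting from treatment". For those participants survival contact runs "thereafter for a total of 48 months after initial dose, or end of the study".

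Analysis. Table 4 lists OS as exploratory for both parts, to be reported if mature. Table 8 in Section 9.4.2 says "OS data may be tabulated and summarized using time-to-event analyses and Kaplan-Meier curves if data is collected and mature", with summaries by cohort within each part. The text after the table censors living participants at the last study assessment if active, or when last known alive if in follow-up. No truncation time or landmark is given.

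Late deaths. Appendix 2, Section 5.1 wants every death after the adverse event reporting period recorded on a survival form. It schedules no matching contact with people who are alive.

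**The concern.** Kaplan-Meier needs censoring that is unrelated to prognosis. Here the length of scheduled follow-up depends on whether a participant was judged to be benefitting at month 24. Survivors who do not extend drop out of scheduled survival contact at about that time, while extenders stay in. A curve labelled as cohort OS would then describe mostly a selected subgroup from that point on.

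Late death reporting does not repair this. If some non-extender deaths after month 24 are entered as events while living non-extenders stay censored at their last contact, the error is pulled downward instead.

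At stake is the reading of a late plateau or drop in the OS curve. The response endpoints and progression-free survival are not touched.

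**Working it through.** **Plan's own figure.** Section 4.1.1 gives up to 27 months per participant. Treatment to month 24 plus the 90-day contact: 24 + 90/30.44 = 26.96 months from first dose. So the last scheduled survival contact of a non-extender dosed until about month 24 falls near month 27.

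**Inputs.** The documents supply the 24- and 48-month horizons, extension conditional on benefit, and the censoring rule. They supply no survival rates and no extension share, and cohort sizes are redacted. All of the following are assumptions:
- Survival at month 24 is 0.30, with exponential survival afterwards.
- p is the share of month-24 survivors who extend; mE and mO are the later median survival times (months) of extenders and others.
- q is the share of non-extender deaths in months 24–48 that is reported.
- Living non-extenders are censored at month 24.
- n = 40 per cohort, range 20 to 60. As a rough guide, the planned total of 270–280 less the Appendix 10 cap of 60, split over five cohorts, gives (270 − 60)/5 = 42 to (280 − 60)/5 = 44.

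**Formulas.** With e(t) = 2^(−(t−24)/mE) and o(t) = 2^(−(t−24)/mO):
- True S(t) = 0.30 × [p·e + (1−p)·o]
- KM(t) = 0.30 × [p·e + (1−p)·q·(o(t) − o(48))] / [p + (1−p)·q·(1 − o(48))]
- With q = 0 this reduces to KM(t) = 0.30 × e(t), the extenders' curve scaled to month 24.

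**Example.** p = 0.3, medians 60 and 12, month 48: e = 0.758, o = 0.25. True = 0.30 × (0.3 × 0.758 + 0.7 × 0.25) = 0.121. KM with q = 0 is 0.30 × 0.758 = 0.227.

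| p; mE/mO | q | KM at 36 / 48 months | True at 36 / 48 months |
|---|---|---|---|
| 0.3; 60/12 | 0 | 26.1% / 22.7% | 18.3% / 12.1% |
| 0.3; 60/12 | 0.25 | 21.2% / 15.8% | 18.3% / 12.1% |
| 0.3; 60/12 | 0.5 | 18.6% / 12.1% | 18.3% / 12.1% |
| 0.3; 60/12 | 1 | 15.9% / 8.3% | 18.3% / 12.1% |
| 0.5; 36/18 | 0 | 23.8% / 18.9% | 21.4% / 15.4% |
| 0.5; 24/18 | 0 | 21.2% / 15.0% | 20.1% / 13.5% |
| 0.3; 24/24 | 0 | 21.2% / 15.0% | 21.2% / 15.0% |
| 0.3; 24/24 | 1 | 16.5% / 6.9% | 21.2% / 15.0% |

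The sign changes with q. The near match at q = 0.5 in the first case is coincidence.

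**Against sampling error.** For q = 0, Greenwood SE = S × √[0.7/(0.3n) + (1−e)/(0.3·n·p·e)]. In the first case at n = 40, 0.3 × 40 × 0.3 = 3.6 extenders are at risk after month 24. The SE is 8.2 points at month 36 and 8.7 at month 48, so the biases of 7.8 and 10.7 points are 0.9 and 1.2 SE. They are 0.7/0.9 SE at n = 20 and 1.2/1.5 SE at n = 60. The largest downward bias (8.1 points at month 48; equal hazards, q = 1) has SE 0.0692 × √(0.0583 + 1/1.8 − 1/7.8) = 4.8 points at n = 40, or 1.7 SE; at n = 60 it is 2.1 SE.

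**The case against.** The case against has real weight.

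- **Status of the analysis.** OS is exploratory, the Kaplan-Meier summary is optional, there is no hypothesis test, and no month-36 or month-48 estimate is promised. Section 9.5 names OS among endpoints that may overrule futility, but the earliest interim needs only 18 weeks of follow-up and no rule uses OS after month 24. This stands and limits the point to minor.
- **Non-extenders may not vanish.** Table 1 footnote 6 continues scans every 12 weeks after the first year until the later of progression and treatment discontinuation (or new therapy or death), and states no month-24 cap. A non-extender who stopped without progressing could still be seen, which moves the date last known alive. The 27-month limit in Section 4.1.1 may restrict this. It softens the loss of follow-up but leaves a selected group, so the table above shows the extreme of complete loss.
- **Magnitudes are assumed.** This stands. The cohort size is also rough: B3 is conditional, and Part A may add participants beyond the cap of 60. At n = 40 every case lies within one cohort's 95% interval. Imprecision does not, however, make the curve estimate the right quantity.
- **Truncation discards data.** Numbers at risk plus a note on unequal contact would already warn a reader. That is a fair lesser alternative, but truncation gives a curve with one clear meaning, and extender data can still be reported separately.

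**Conclusion.** The point holds as a minor analysis issue. Follow-up after month 24 depends on extension, extension depends on benefit, and the OS analysis does not account for it. In a cohort with extenders, the curve beyond about month 24 may not be interpretable as cohort survival. A cohort without extenders has no such tail.

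Two stronger readings are tempting and not supported. A reader might infer that the late curve is necessarily wrong, or necessarily too high. With equal later hazards and no late reporting the bias is zero, and with late deaths reported it can be negative; under the assumptions used it runs from about −8 to +11 points at month 48. A reader might also infer that the curve already fails before month 24, because quarterly contacts are counted from last dose and an early stopper's last contact can fall in months 21–24. Under an assumed even spread of last contacts, that shifts the month-24 estimate by only +1.2 to −2.4 points against an SE of 7.2 at n = 40. This is too small and too dependent on the assumption to justify an earlier cut.

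**What to change.** In Section 9.4.2, state that the by-cohort OS Kaplan-Meier analysis is truncated at month 24 from first dose: each participant is censored at the earlier of the date last known alive and month 24, and later deaths are listed but are not events in this analysis. Show numbers at risk. Describe extenders' later survival separately, from a month-24 landmark.

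Optionally, in Section 8.10.4.2, time the last scheduled contact of non-extenders at month 24 so that vital status is known at the cut. Contact by phone is already allowed. In an assumed cohort of 40 with 30% alive at month 24 (12 people) and 30–50% of them extending, that is about 6 to 8 calls.

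The cost is a few sentences in Section 9.4.2 and, if the option is taken, one in Section 8.10.4.2. The downside is that extender follow-up after month 24 no longer contributes to the cohort curve.
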